7. STUDY DESIGN

7.1. OVERALL DESIGN

This study is a multi-site, sequential, multiple assignment randomized trial (SMART) to estimate DTRs based on four evidence-based interventions for chronic low-back pain. The trial is designed to meet the primary objective of estimating an algorithm for optimally assigning treatments based on an individual patient's phenotypic markers and response to treatment. Interventions being evaluated in this trial are: (1) enhanced self-care (ESC), (2) acceptance and commitment therapy (ACT), (3) duloxetine, and (4) evidence-based exercise and manual therapy (EBEM).

Each participant will complete an initial screening call and enrollment visit, followed by a 2-week run-in period, post run-in eligibility screening, two consecutive 12-week treatment periods, and a minimum of 4 weeks of follow-up. Participants will be screened using a combination of telephone assessments prior to, and in-person evaluation during, an initial screening period. Eligible participants who provide consent to participate will be enrolled and enter a 2-week run-in period focused on patient engagement. The goals of the run-in are to engage individuals from diverse backgrounds, educate potential participants about the study, assess adherence and engagement prior to randomization, enhance retention, and establish communication between participants and members of the study team. In the first treatment period, participants will be randomly assigned at Visit 0 to one of the four study interventions. For the second treatment period, depending on response to their initial treatment, participants will be assigned to: (1) maintain their current intervention, (2) augment their current intervention with another study intervention, or (3) switch to a new study intervention. For treatment actions (2) and (3), the additional or new intervention will be randomly determined independent of participant response to the initial treatment. Patient Reported Outcome (PRO) assessments will be performed at baseline (Visit 0/Week 0) and at Weeks 6, 12, 18, 24, and 36, and phenotyping will be performed at baseline (Visit 0/Week 0) and at Weeks 12 and 24 (Visits 1 and 2)

At the end of the run-in period, participants will be re-assessed for eligibility. Those meeting requirements for randomization (Section 8) will be randomized to one of the 4 first line treatments. At the baseline visit (Visit 0), all participants will undergo baseline data collection and phenotyping. Data collected for phenotyping will include patient-reported outcomes, spinal imaging, biomechanical assessments, and collection of blood and stool. As described in Section 5.2.2, some of these data will be collected at home prior to the in-person portion of the study visit. A subset of eligible and willing participants (~n=200) will undergo additional phenotyping. Details of the phenotyping assessments are available in Section 9. A subset of phenotypic markers will be re-assessed Week 12 (Visit 1) and Week 24 (Visit 2).

Participants will be assessed for response to treatment Week 12 (Visit 1) and Week 24 (Visit 2) using the PGIC and PEG. Participants will be grouped into one of four responder classes using the PGIC and PEG (see Section 7.1) and assigned to the following based on their responses:

- maintain current treatment (PGIC=1-2, PEG <4),
- augment the current treatment with a randomly selected additional treatment (PGIC=1-2, PEG ≥4),
- be randomized to augmentation or switching to a new treatment (PGIC=3-4), or
- switch to a randomly selected new treatment (PGIC=5-7)

Since the ESC modules focus on self-care, education and a walking program, requiring participants in this intervention arm to cease these activities is not practical; therefore, individuals assigned to ESC at the first randomization will maintain ESC if PGIC is 1-2 and PEG<4 else they will augment ESC with a randomly selected additional treatment. Participants who wish to discontinue treatment but whose

PGIC is less than 6 and who are not contraindicated to their current treatment will be asked to continue first-line treatment until the end of the 12-week treatment period.

All participants will also receive an assessment 4 weeks after the end of the second treatment period for safety purposes (week 28). Participants, whose randomization to the first intervention is at least 36 weeks prior to the end of data collection, will be assessed for outcomes at 36 weeks.

Participants may need to discontinue treatments prior to the end of the 12-week treatment period (e.g., following an adverse reaction to duloxetine; see Section 10.2.1 for list of reasons). Participants needing to discontinue first period treatment will be switched to a randomly selected second treatment at Visit 1. Participants needing to discontinue second period treatment will remain in the study and undergo all future assessments for which they are eligible.

The study will enroll approximately 820 participants in order to randomize approximately 740 individuals and to have approximately 630 completers (i.e., 15% dropout rate after randomization assumed). Assuming dropout occurs uniformly across study interventions, the sample size of 740 randomized will result in having approximately 80% probability of estimating a DTR within 90% of the optimal DTR based on the study's primary endpoint. See Section 13.2 for additional details on sample size needs for precision medicine objectives, including assumptions regarding intervention effect sizes.

The interventions under evaluation are evidence-based, with established efficacy and are standard of care. Therefore, we do not expect they will pose safety risks such that these interventions need to be stopped before the end of the study. Safety data and adverse events will be monitored. These data will be reported to and reviewed by a Data Safety and Monitoring Board. Generally, this trial will inform a precision medicine approach to the treatment of chronic low-back pain and therefore we are not planning interim analyses for futility or efficacy in order to maintain sufficient power for the precision medicine analyses. Blinding is not feasible for study participants or staff involved in the delivery of interventions. Investigators involved in the analysis of study data will be blinded to treatment assignment.

The study timeline involves approximately 9 months of participant enrollment across 12 sites for a total of 820 enrolled. Sites will enroll ~7 participants per month. We anticipate that ~90% of participants who consent at the Enrollment Visit will be randomized at the end of the 2-week run-in at Visit 0 and that 85% of randomized participants will complete all study activities. The total study duration for all participants is 38 weeks. To minimize participant burden, where possible, data will be collected remotely.

7.2. SCIENTIFIC RATIONALE FOR STUDY DESIGN

As described above, this trial will inform a precision medicine approach to the treatment of cLBP. This goal is motivated by the observation that, while numerous treatments exist for cLBP, all are associated with relatively small population average treatment effect sizes. This study seeks to understand how to better match future patients to the most appropriate treatment based on their phenotypic measures to optimize outcomes. To achieve this goal, we have chosen to conduct a sequential, multiple assignment, randomized trial (SMART).

7.3. JUSTIFICATION FOR DOSE/INTERVENTION REGIMENS

The justifications for doses for individual treatments are found in Sections 10.

7.4. END OF STUDY DEFINITION

For study non-completers, the end of the study will coincide with the point in time when the participant notifies study personnel that they wish to discontinue the study. If the reason for study discontinuation is related to an incidence adverse event, and if the participant consents to further contact by study staff, the participant will be contacted by phone 4 weeks after completion of the study discontinuation visit to follow up on adverse events and document their resolution or status.

The study will end approximately 38 weeks after randomization (at the time of completion of the 12-week post-intervention follow-up period).

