Any medical condition that is present at the time that the participant is screened will be considered as baseline and not reported as an AE. However, if the study participant's condition deteriorates at any time during the study, it will be recorded as an AE.

Changes in the severity of an AE will be documented to allow an assessment of the duration of the event at each level of severity to be performed. AEs characterized as intermittent require documentation of onset and duration of each episode.

A site physician investigator or sub-investigator will record all reportable events between the time the participant provides informed consent through 4 weeks after their last treatment. At each study visit,

the investigator will inquire about the occurrence of AE/SAEs since the last visit. Events will be followed for outcome information until resolution, stabilization, or participant is off-study.

12.3.5.ADVERSE EVENT REPORTING

Serious Adverse Event Reporting

Study investigators will immediately notify the DAC of any serious adverse event, whether or not considered test treatment-related, including those listed in the protocol or investigator brochure. The report must include an assessment of whether there is a reasonable possibility that the treatment caused the event.

All serious adverse events (SAEs) will be followed until satisfactory resolution or until the site investigator deems the event to be chronic or the participant is stable. Other supporting documentation of the event may be requested by the DAC and should be provided as soon as possible.

- All AEs will be reported in aggregate to the NIAMS and the DSMB (through the NIAMS Executive Secretary) as part of the routine DSM report.
- All SAEs (regardless of relatedness or expectedness) will be reported to the NIAMS and the DSMB (through the NIAMS Executive Secretary) within 48 hours of the investigator becoming aware of the event.

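### Protocol 12.3.4 sets one adverse event window for everyone, but 7.4 schedules a contact after early exit only for consenting leavers whose reason is an adverse event

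*Protocol*

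**What the plan says.** **Recording window.** Protocol Section 12.3.4 says that the responsible staff at each site "will record all reportable events between the time the participant provides informed consent through 4 weeks after their last treatment". It draws no distinction by reason for leaving. It adds: "Events will be followed for outcome information until resolution, stabilization, or participant is off-study".

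**Early exit.** Section 7.4 says that, for anyone who leaves early, "the end of the study will coincide with the point in time when the participant notifies study personnel that they wish to discontinue the study". A later contact depends on two conditions: "If the reason for study discontinuation is related to an incidence adverse event, and if the participant consents to further contact by study staff". If both are met, "the participant will be contacted by phone 4 weeks after completion of the study discontinuation visit to follow up on adverse events", and the call also serves to record how those events turned out.

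**Withdrawal and taper.** Section 11.2 provides a termination visit when consent is withdrawn. A participant on duloxetine who leaves the whole study is advised either to taper as in Section 10.2 or to obtain a prescription elsewhere. Section 10.2.1 gives a standard taper of up to two weeks, which can be extended by one.

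**Reporting.** Section 13.4.4 limits safety analysis to descriptive summaries and listings. The SAP's Appendix 3 tables show affected over at-risk participants by treatment, for 805 participants randomized to Stage 1 and 683 randomized to Stage 2. The SAP gives no rule for participants observed for less than the full window.

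**The concern.** Whether anyone is contacted after exit depends on whether an adverse event was the reason for exit, and adverse events are what the safety tables count. A person who leaves because of burden, lack of benefit or a move is inside the 12.3.4 window but has no contact scheduled in it.

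Reasons for leaving could plausibly differ between a drug arm and a digital self-care arm. If they do, arms with the same true risk after exit could show different event percentages. The tables as laid out would not reveal this, because they show neither observation time nor exit reason. The gap also bears on participant safety: someone can be advised to taper study drug after their study has formally ended, with no call planned.

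**Working it through.** **1. Does another provision reach the leaver whose reason is not an adverse event?**

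- *Week-28 safety assessment (5.2.3, 7.1):* tied to the end of the second treatment period. It does not follow an early leaver's own last treatment, and under 7.4 that person's study is already over.
- *Termination visit (11.2):* covers events up to exit.
- *Lost to follow-up (11.3):* contact attempts and a termination form, with no safety window.
- *Stopping treatment but staying in the study (4.1, 7.1, 12.2):* assessments continue, so this group is outside the point.
- *Serious events (12.3.5):* "All serious adverse events (SAEs) will be followed until satisfactory resolution", whatever the exit reason, but this concerns events already known.
- *Off-study clause (12.3.4):* limits outcome follow-up of recorded events. It does not shorten the recording window.

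None of these gives that person a contact after exit.

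**2. Length of the gap.** Let L be the day of last treatment and E the day of exit. The 12.3.4 window closes at L + 28, so the part without scheduled contact is max(0, L + 28 − E) days.

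- Exit on the day of last treatment (E = L): 28 days.
- Exit 28 or more days after last treatment: 0 days.
- Exit followed by a duloxetine taper, if taper doses count as treatment (the protocol does not say): L = E + 14 gives 42 days, and L = E + 21 gives 49 days.

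The taper case also shows that the two clocks differ for those who do get the call. If the discontinuation visit is on day E, the call falls at E + 28, which is 14 to 21 days before the window closes.

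**3. Size of the group.** Section 7.1 plans 740 randomized and 630 completers: 740 − 630 = 110, or 110/740 = 14.9%. As a check, 630/0.85 = 741.2, rounded up to 742, which agrees with the stated approximate 740. Under the plan's own dropout assumption, 110 is an upper bound on those affected:

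- Section 13.2 calls the 15% an upper bound rather than the expected dropout.
- Section 10.4.4 describes it as loss to follow-up. Under 11.3 such people do not respond to contact, so they give no notice under 7.4 and a call to those who agree would not reach them.
- Some leavers' windows have already closed. ACT sessions are scheduled through week 7 and EBEM visits usually through week 8. If those mark last treatment, the windows close at weeks 11 and 12.

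The SAP's 805 − 683 = 122 (15.2%) not randomized to Stage 2 is not a count of withdrawals, because no reasons are given.

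**4. Illustration on assumed rates.** Take about 201 per arm and 15% leaving: 0.15 × 201 = 30.15. Assume that all of them are inside the window, with a true post-exit event risk r that does not depend on exit reason. Let s be the share leaving because of an adverse event, all of whom agree to a call that captures every event. Then missed = 30.15 × r × (1 − s).

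| r | s | missed | points of the arm |
|---|---|---|---|
| 5% | 50% | 0.75 | 0.4 |
| 10% | 50% | 1.5 | 0.75 |
| 10% | 5% | 2.9 | 1.4 |
| 20% | 5% | 5.7 | 2.9 |

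At r = 10%, an arm with s = 50% would capture 1.5 of 3.0 affected participants and an arm with s = 5% would capture 0.15 of 3.0, although the true risk is equal. The documents supply neither r nor s.

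**The case against.** The best defence is that the 7.4 call is follow-up of known events, as its wording on resolution or status suggests, so it naturally applies only to people who have one. Section 12.3.4 is a duty to record what comes to light, and it lists visits, presentations for care and monitor review as routes. Section 7.4 forbids neither recording nor contact, and people who withdraw consent may not be contactable.

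Much of this stands, and it rules out two stronger readings. A reader might infer that the two sections cannot both be followed. The text shows a window with no scheduled contact, not an impossibility. A reader might also infer that adverse event leavers are fully covered. They are not: they must agree to the call, it is timed from a different point, and capture of new events on it is not spelled out.

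The defence does not remove the mismatch. Section 7.4 itself accepts contact by agreement after exit and offers it to one group only. No passage gives a willing leaver from the other group any scheduled contact in a window that 12.3.4 applies to everyone.

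**Conclusion.** The mismatch is in the current text and should be corrected. It concerns participants who leave the study altogether, for a reason other than an adverse event, within 4 weeks of last treatment.

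The number affected cannot be derived. A reader might assume that 10% to 30% of the 110 leave because of an adverse event and conclude that 110 × 0.70 = 77 to 110 × 0.90 = 99 people have no coverage. The documents do not support that: the share is assumed, and the 110 includes people lost to follow-up and people whose window had already closed.

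Nor do the documents show that any arm's percentages are in fact biased. They show that capture after exit can differ by arm if reasons for leaving do. The consequence is confined to descriptive safety tables. The SAP plans no hypothesis tests, and the primary estimand is untouched.

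**What to change.** Reconcile Protocol Sections 7.4, 11.2 and 12.3.4 so that one post-exit adverse event window, with one stated starting point, applies to all treated leavers who agree to contact, whatever their reason for leaving. The reconciled text should say how a taper after exit relates to that starting point. The choice of window and starting point belongs to the sponsor and investigators.

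The SAP already reports completed randomization counts, so much of the remedy lies in reporting. In Appendix 3, give by arm the number who left before the 12.3.4 window closed, and note that post-exit contact depended on the reason for leaving. Cutting off at-risk time is not a ready alternative, because the tables hold participant counts and no person-time.

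The cost is a short protocol clarification, at most one call by existing site staff per consenting leaver, and an added table row or footnote.

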8. STUDY POPULATION

8.1. STUDY INCLUSION CRITERIA

To be eligible, an individual must meet all of the following inclusion criteria:

- Ability to read and understand English
- Provision of signed and dated informed consent form(s)
- Willing and able to receive study-related messages and survey links via email
- Willing and able to receive study-related phone calls
- Age 18 years old or older
- Low-back pain for at least 3 months and occurring on at least half the days in the past 6 months
- Contraindicated to no more than one of the study interventions at the time of eligibility assessment(s)
- Eligible to receive at least three of the four study interventions and willing to receive any intervention for which they are eligible
- A PEG score 4 or higher prior to the Run-in period
- Willing and able to undergo required phenotyping as defined in Section 9
- Regular reliable access to an internet-enabled device such as a smart phone, tablet, or laptop computer
- Meet Run-in period engagement eligibility criteria:
 - Completion of two Run-in study information modules prior to period 1 randomization (Visit 0)
- Low-back pain more severe than pain in other parts of the body
- Available to complete the full study protocol (approximately 9 months)

8.2. STUDY EXCLUSION CRITERIA

An individual who meets any of the following criteria will be excluded from participation in this study:

- Pregnant at the time of Visit 0 (Baseline)
- Affirmative participant response to any of the following conditions:
 - Progressive neurodegenerative disease
 - History of discitis osteomyelitis (spine infection) or spine tumor

- History of ankylosing spondylitis, rheumatoid arthritis, polymyalgia rheumatica, psoriatic arthritis, or lupus
- History of cauda equina syndrome or spinal radiculopathy with functional motor deficit (strength <4/5 on manual motor testing)
- Diagnosis of any vertebral fracture in the last 6 months
- Osteoporosis requiring pharmacologic treatment other than vitamin D, calcium supplements, or bisphosphonates.
- History of any bone-related cancer or cancer that metastasized to the bone
- Currently in treatment for any non-skin cancer or plan to start non-skin cancer treatment in the next 12 months
- History of any non-skin cancer treatment in the last 24 months
- Visual or hearing difficulties that would preclude participation
- Uncontrolled drug/alcohol addiction
- Individuals actively pursuing disability or workers compensation or involved in active personal injury-related litigation
- o Currently participating in another interventional pain study
- Any condition that, in the opinion of the investigator, would preclude the patient from being able to safely participate in in the trial

8.3. STUDY INTERVENTION CONTRAINDICATIONS

ACT intervention contraindications

An individual who meets any of the following criteria will be excluded from being randomized to receive ACT during the study:

Currently receiving or intending to receive within the next few months any pain-specific
psychotherapy, e.g., Cognitive Behavioral Therapy, directed towards pain even if it is only a part
of the treatment, and delivered by a psychologist or social worker

Duloxetine intervention contraindications

An individual who meets any of the following criteria will be excluded from being randomized to receive duloxetine during the study:

- Pregnant: If the participant becomes pregnant during the study, duloxetine will be rapidly tapered.
- Currently taking any of the following:

Duloxetine

Lithium

Tramadol (Ultram, Ultracet)

St. John's Wort

Prochlorperazine (Compazine)

Thioridazine (a psychiatric medication)

Propafenone or Flecainide (for heart rhythm problems)

Ciprofloxacin (Cipro, an antibiotic)

Linezolid (Zyvox, an antibiotic)

Methylene Blue

Cimetidine (Tagamet, for heartburn)

Bupropion (Wellbutrin)

SNRIs:

Venlafaxine

Milnacipran

Duloxetine

Sibutramine

Atomoxetine

Desvenlafaxine

Levomilnacipran

SSRIs:

Sertraline

Paroxetine

fluoxetine

escitalopram

citalopram

fluvoxamine

Vortioxetine (Trintellix)

Any other contraindicated SNRIs, SSRIs, and antidepressants

Reporting a current or previous diagnosis of any of the following

Renal dysfunction

End-Stage Renal Failure

Hepatic dysfunction

- Previous allergic or other severe adverse reaction to duloxetine or, as determined by the site PI, a medicine with duloxetine cross-reactivity.
- History of bipolar disorder, manic episodes, or suicide attempts
- Currently breastfeeding

EBEM intervention contraindications

An individual who meets any of the following criteria will be excluded from being randomized to receive EBEM during the study:

- Currently receiving or intending to receive within the next few months any type of manual therapy or exercise treatment for low-back pain from a licensed provider
- Uncontrolled high blood pressure (≥150 systolic and/or ≥100 diastolic)
- Uncontrolled coronary artery disease
- Inability to walk at least 50 feet unassisted
- Contraindication for manual therapy
- Contraindication for participation in an exercise program

ESC intervention contraindications

An individual who becomes pregnant during the study will be counseled to stop NSAIDs.

